Results and Discussion: Data will be presented as mean value (+/- SD) while $p < 0.05$ will be considered significant. Mixed Analysis of Variance will be used for comparisons between and within group. There will be no significant difference in lung compliance between groups before RM ($p > 0.05$). Two-sample t-test to compare the two groups at each time point will be used as supplementary analysis, while chi-square test for categorical variables and two-sample t-test for continuous variables for patient and procedural characteristics differences between the two groups, will be used. In the RM group, according to similar studies, the investigators are expecting to see a significant increase in lung compliance after RM compared to control group were RM was not applied. In the RM group the investigators estimate that dynamic lung compliance will be significantly higher at all time points (3 minutes, 10 and 20 minutes) compared to baseline compliance or compliance before RM too. In the control group there should be no significant difference in dynamic lung compliance at the different time points. There should be no significant demographic differences between groups while the investigators estimate that there will be no statistical or/and clinical significant differences in SpO_2 , blood gas, end-tidal CO_2 , Ppeak, and women hemodynamic.

Introduction

General anesthesia (GA) can cause changes in respiratory mechanics and lung function, which persist for days after surgery. These changes occur immediately after induction of anesthesia but are aggravated with mechanical ventilation¹⁻⁵. The reduction in lung compliance and the formation of atelectasis after the induction of GA is a significant cause of abnormalities in regional ventilation and gas exchange⁴. Two different types of atelectasis, compression atelectasis and resorption atelectasis, have an impact on patient's condition. The reduced activity of the diaphragm and the weight of lung or abdominal organs in the supine position promote the formation of compression atelectasis.

Atelectasis formation

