Our power analysis is based on previous studies but is even more generous^{17,22}. The required sample size calculation was based on the following assumptions: Clinically meaningful difference between the two groups is 20% of the mean value, and SD of the observed lung compliance is 25% of the mean value (rather generous), therefore size effect $d = 20\% / 25\% = 0.8$, with two-sided testing, with $\alpha = 0.05$ and $b = 0.1$ (therefore, power = $1 - b = 0.9$). Under these assumptions, G*Power indicated that we will need minimum 34 patients per group for this study to have adequate power. To confirm accuracy of this calculation, we will also conduct sample size estimation using the Statistica v 7.0 Statistical Software package (StatSoft Inc, Tulsa, Oklahome, USA), in order to find out if this confirmatory analysis will produce identical results. Finally we will confirm our results using the suitable mathematic formula (see [appendix 2](#)).

In order to allow for possible protocol violations, errors, patient attrition or other study shortcomings, we will enroll 45 patients in each arm of the study (about 10 women more in each group of patients). As pregnant women are a very “sensitive” population and we are afraid of much protocol violation (removal women from protocol mainly due to hemodynamic instability) we will chose to randomize 45 women per group, which is a generous number.

We will check if data are normally distributed (Kolmogorov Smirnov and Shapiro Wilks test). Ventilatory and haemodynamic data and intraoperative and postoperative variables (all continuous variables) will be presented as mean values (+/- SD). Data will be compared between and within groups using Mixed Analysis of Variance (Mixed Anova-General Linear Model) if are normally distributed or with Kruskal Wallis test in case that we do not have normally distributed data.

Bonferoni correction will be used for multiple comparisons correction. In order to check and supplement our Mixed Analysis of Variance we will also use two-sample t-test to compare the two groups at each time point (for ventilatory and haemodynamic variables). Patient and procedural characteristics will be compared between groups using chi-square test for categorical variables and independent-sample t-test for continuous variables. Two tailed P-values <0.05 will be considered statistically significant. For data analysis SPSS statistical software version 22 will be used.

Patients Records

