For each patient we will have four data files:

1. Demographic intra- and post-operative patient data (appendix 3)
2. Mechanical ventilation data (appendix 4)
3. Haemodynamic data (appendix 5)
4. Blood gas data (appendix 6)

Data Presentation Plan

Number of eligible women and number of women excluded before randomization (lets say X):

Possible reasons for exclusion:

[figure not shown]
X1 women could decline participation and choose regional anesthesia, X2 could have emergency surgery, X3 will have active asthma, X4 will have BMI >40, X4 will be < 18 years old, X5 will suffer arterial hypertension etc. If we add: $X1+X2+X3+X4+X5+... Xi=X$

Finally we will include 45 patients in each group.

Number of women that will complete the study = F (For example 40 women in the RM group and 41 women in the Control group)

Give reasons for not complete the study: Heart rate >110bpm, Low arterial blood pressure, hypertension, asthmatic attack during the surgical procedure etc.

Flow chart:

If all, or almost all of the patients will complete the study (we will have the most of the measurements in each time point) we will use a per protocol analysis. If we have many missing data we will use an intention to treat analysis of data (ITT). According to ITT analysis of data I will use all the data of all the randomized patients regardless of whether they completed the trial or not. For the missing values I will use the “last observation carried forward” (LOCF) approach

Patient characteristics should be similar between the two groups (table 1). If not we will have to mention the differences and this would be a serious limitation of our study.

Intraoperative characteristics (time to delivery, anesthesia duration, estimated blood lose, administration of crystalloids and/or colloids, administration of blood products and intraoperative use of ephedrine should be similar between the two groups (table 1).

The length of hospital stay and the possible differences between the two groups should be mentioned (table 1). The number of patients that will suffer postoperative pulmonary complications (mainly pneumonia, diagnosed with chest radiogram and clinical evaluation) and possible differences between the two groups should also be mentioned. Pneumothorax would be a serious adverse event, which could have a strong relationship with the RM manipulation of the patients and should be recorded. See adverse event section below.

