Table 1: Patient characteristics presented as mean (SD) or n=number of patients. Intra- and post-operative characteristics presented as mean (SD).

Patient Characteristics	RM Group n=45	Control Group n=45
Age (yrs.) [mean (SD)]	A1	B1
BMI (kg/m ²) [mean (SD)]	A2	B2
Smoking status (n)	A3	B3
Intraoperative Characteristics		
Duration of anesthesia (min)	A4	B4
Time to delivery (min)	A5	B5
Crystalloids (ml)	A6	B6
Colloids (ml)	A7	B7
Blood (units)*	A8	B8
Ephedrine dose (mg) ⁺	A9	B9
Postoperative Characteristics		
Length of hospital stay (days)	A10	B10
Pulmonary complications (n)	A11	B11
Pneumothorax (n)	A12	B12
Pneumonia (n)	A13	B13
Other (n)	A14	B14

Efficacy and Safety issues:

The efficacy of the RM to improve lung compliance and gas exchange will be the main efficacy issues of the study. The investigators believe that the Com_{dyn} (dv/dp) will be statistical significantly improved in the RM group compared to the control group (statistical significant difference between groups). A 20% increase in mean Com_{dyn} in the RM group compared to the control group would be clinically significant. This change in lung compliance perhaps would not have any significant impact for the majority of the patients of our study (young and healthy patients). However, underlying comorbidities may amplify changes in lung and cardiovascular physiology and anaesthesia may serve as a 'second-hit' that worsens patient outcome. For this reason a RM and the application of protective lung ventilation (low tidal volumes and PEEP) perhaps should be the suitable anesthetic practice for all the patients.

The investigators also believe that there would be statistical significant difference within groups too. In the RM group possibly there would be a difference in lung compliance (increase) between baseline and all the other time points (3, 10 and 20 minutes after the RM). Again a 20% increase in Com_{dyn} would be clinically significant, at least for some patients.

The investigators believe that the recruitment manoeuvre will improve the intraoperative and/or postoperative PO_2 , the PO_2/FiO_2 and the SpO_2 . Again for the population of our study (all women have a baseline $PO_2/FiO_2 > 400$) this improvement will not have a significant impact. All the data will be presented in tables 2 and 3 (**see next example with preliminary data analysis**).

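### Patient characteristics and pre-RM readings are significance-tested at P<0.05, which neither shows a flaw nor shows balance in a randomised trial, and no adjustment for baseline Com_dyn is named

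*Protocol*

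**What the plan says.** Four places in the protocol bear on this.

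- Statistical analysis: "Patient and procedural characteristics will be compared between groups using chi-square test for categorical variables and independent-sample t-test for continuous variables". The threshold follows: "Two tailed P-values <0.05 will be considered statistically significant". The same section adds two-sample t-tests at each time point for ventilatory and haemodynamic variables. It also announces a Bonferroni correction without saying which comparisons it covers.
- Abstract, Results and Discussion: "There should be no significant demographic differences between groups", and for the primary variable, "There will be no significant difference in lung compliance between groups before RM", with p > 0.05 given in brackets.
- Data Presentation Plan: patient characteristics in Table 1 should be similar, and "If not we will have to mention the differences and this would be a serious limitation of our study". The sentence gives no threshold of its own. Table 1 lists three patient characteristics: age, BMI and smoking status.
- Preliminary Data Results, Table 2 (the example of the planned presentation): the P-value is the between-subject main effect of the mixed ANOVA, and baseline is listed beside 3, 10 and 20 minutes. Unadjusted t-tests are made at separate time points. Neither this table nor the Statistical analysis section names an adjustment for baseline Com_dyn.

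**The concern.** Allocation is by computer-generated blocks in sealed envelopes (Randomization), and both groups are ventilated identically until after delivery (Ventilatory Management). If that is carried out correctly, differences between the randomised groups before the RM arise by chance. A test of whether they arose by chance has no useful hypothesis to reject. A small P-value does not show that the comparison is damaged, and a large one does not show that the groups are balanced on what matters.

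Two things are at stake. A sound trial may label itself seriously limited because one of a few characteristics happened to cross 0.05. And a baseline Com_dyn difference large enough to matter may go unflagged, while the planned comparison of the primary endpoint contains nothing that would remove it.

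**Working it through.** **Inputs.** 45 per group (Randomization); two-sided 0.05, SD 25% of the mean and target difference 20% of the mean (Statistical analysis); three patient characteristics (Table 1). Correlations and smoking prevalences below are assumptions, since the protocol gives none.

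**1. The plan's own figure.** Appendix 2: n ≥ 2 × (25/20)² × (1.96 + 1.28)² = 32.8, so 33 per group. The noncentral t calculation gives 34 (power 0.9015; 33 gives 0.893), matching the G*Power figure. The design inputs are therefore read as the plan intends.

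**2. Chance of a false alarm.** With three independent tests of exact 5% size and correct randomisation: 1 − 0.95³ = 0.143.

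| Assumption | Chance of at least one P<0.05 |
|---|---|
| Independent, uncorrected | 14.3% |
| All pairwise correlations 0.3 / 0.5 / 0.8 (simulated) | 13.5% / 12.5% / 9.7% |
| Uncorrected chi-square, smoking prevalence 2% / 5% / 10% / 20–30% | 10.7% / 14.2% / 15.1% / 14.6% |
| Continuity-corrected chi-square, prevalence 2–30% | 9.8–12.4% |
| Bonferroni over the three tests: 1 − (1 − 0.05/3)³ | 4.9% |

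**3. Imbalance that passes.** Largest non-significant difference at 45 per group: t(0.975, 88 df) × √(2/45) = 1.987 × 0.2108 = 0.419 SD. For Com_dyn, 0.419 × 25% = 10.5% of the mean, and 10.5/20 = 0.52 of the target. For smoking, 9 versus 17 of 45 gives an uncorrected chi-square of 90 × (8 × 45)² / (45 × 45 × 26 × 64) = 3.46, below 3.84, so 20% versus 38% smokers also passes.

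**4. How often this occurs.** The standard error of the baseline difference is 25% × 0.2108 = 5.27% of the mean, so the median absolute difference is about 0.674 × 5.27% = 3.55%. In simulation, a difference above 10% that is also non-significant arises in about 1.2% of trials.

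**5. What reaches the primary comparison.** In an unadjusted post-RM comparison, a baseline gap carries over in proportion to the correlation r between baseline and post-RM Com_dyn, if the SDs are similar. Assuming r from 0.5 to 0.9, a 10.5% gap contributes 0.5 × 10.5 = 5.25 to 0.9 × 10.5 = 9.45 percentage points, that is 26% to 47% of the 20% target. With baseline as a covariate, residual variance is multiplied by 1 − r²: 0.75 at r = 0.5 and 0.19 at r = 0.9.

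**6. The protocol's own example.** Table 2 shows baseline Com_dyn of 33.6 versus 31.1, a gap of 2.5/31.1 = 8%, with no significance mark.

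**The case against.** Several points against this are fair.

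- The Data Presentation Plan sentence names no test and no P-value. Reading it as a rule that P<0.05 means a serious limitation requires joining it to the Abstract and the Statistical analysis section. That stands. Significance is, however, the only criterion for similarity found anywhere in the protocol.
- A reader might infer that at least 14% of sound trials would be flagged. The protocol does not support a floor: correlation, a sparse smoking count or the unscoped Bonferroni sentence would each lower the rate. That sentence follows the mixed ANOVA and precedes the characteristics tests, so its coverage of them is doubtful but not excluded. If it did apply, larger imbalances would pass.
- A reader might add the 13 pre-RM readings in Tables 2 and 3 and reach a far higher rate. The limitation sentence covers patient characteristics only, and many of those readings overlap (systolic, diastolic and mean pressure; PaO₂ and its ratio to FiO₂).
- A reader might infer that a non-significant baseline compliance would be taken as proof of balance. The Abstract sentence stands among expected results, and no analysis is made to depend on it.
- Women may be removed after randomisation and a per-protocol set analysed, so differences among those analysed need not be pure chance. This is a reason to look at baseline carefully, but the P-value is a poor instrument for it: at 45 per group a systematic imbalance of 0.4 SD would be flagged only 47% of the time, and one of 0.3 SD only 29%.
- Deleting the tests does not remove an imbalance, and covariates are often left to an analysis plan. The first half is right, which is why the covariate is part of the fix. On the second, the protocol already specifies its between-group comparison, and that comparison is unadjusted.

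**Conclusion.** The point holds in a limited form. The baseline P-values answer no useful question, and the protocol attaches a conclusion about the trial's quality to dissimilarity for which significance is its only stated criterion. The false-alarm rate is about 14% if the three tests are independent and uncorrected, roughly 10–15% over the assumed correlations and smoking prevalences, and about 5% if Bonferroni applies. In the other direction, a baseline Com_dyn gap of up to about 10.5% of the mean can pass. That rests on 45 analysed per group and the plan's SD, and a gap near that limit is uncommon.

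The consequence is moderate. The tests affect how Table 1 is interpreted; they do not alter the primary test, the analysis set or the sample size. The more useful gain is in the primary comparison, where a recorded pre-intervention Com_dyn value is not used as a covariate.

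**What to change.** 1. In the Statistical analysis section, and correspondingly in the Abstract, remove the significance tests on age, BMI and smoking status and the t-tests at the pre-RM reading. Present baseline by group as mean (SD) or counts.
2. Remove or recast the Abstract expectations of no significant demographic and pre-RM compliance differences.
3. In the Data Presentation Plan, delete the limitation sentence or reword it so that balance is judged by the size of a difference and its prognostic relevance.
4. Compare post-RM Com_dyn between groups with baseline Com_dyn as a prespecified covariate, whatever the baseline P-value.
5. Keep between-group comparisons for what happens after the intervention.

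The cost is wording, fewer tests and one covariate that is already recorded. The sample size stays as it is.

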The anesthetic technique will be the same for both groups of patients and is standardized as follows: Anesthesia will be induced with propofol (1.5-2 mg/kg), fentanyl (1 µg/kg) and rocuronium (1.5 mg/kg) and will be maintained with sevoflurane (minimal alveolar concentration 0.6-0.8) and fentanyl (400-450 µg). The minimum alveolar concentration of sevoflurane will be titrated from the attending anesthesiologist according to the arterial blood pressure (\pm 15-20 mmHg baseline) and beats per minute (\pm 10-15 baseline). Rocuronium for muscle paralysis will be used once, during induction of anesthesia to facilitate tracheal intubation (cuffed tube no 7-7.5-Portex, Inc., London) and without subsequent bolus doses, while at the end of the operation sugammadex (200 mg) will be used for neuromuscular block reversal. Intraoperatively ondasetron 4 mg, omeprazole 40 mg, paracetamol 1000 mg and Parecoxib 40 mg will be used to all the patients. The time between the end of preoxygenation and tracheal intubation must be standard (40-60 seconds) and will be recorded for all the patients. The Perioperative use of crystalloids and colloids, blood products and vasopressors will be recorded while fluid management will be left to the discretion of the attending anesthesiologist (Ringers Lactated). Hypotension (mean arterial pressure <60 mmHg) will be treated with ephedrine bolus 5 mg i.v and if insists bolus doses of hydroxyethylstarch (HES 130/0.4, Voluven; Fresenius Kabi, Germany) up to 1000 ml will be given. The standard monitors of the American Society of Anesthesiologists will be used while the radial artery will be cannulated for invasive blood pressure monitoring and blood gas measurements.

[figure not shown]
Ventilatory Management (time and method of RM)

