Because of the higher inspiratory pressures during RM and PEEP used, the $P_{plateau}$ and P_{peak} are anticipated to be significantly higher in the RM group, compared with those in the control group, and this would be a possible serious safety issue, as high alveolar pressures could result in pneumothorax or/and barotrauma. As the study involves young and healthy population, the investigators believe that the above safety issues will not be a serious problem of the study. A second safety issue will be the hemodynamic instability during RM. Patients with serious hemodynamic instability will be removed from the study, as already mentioned.

End of treatment

The treatment (RM) will start after delivery (3 minutes) and will last until the end of the surgery. Specifically, in the RM group the RM will be performed 3 minutes after delivery but PEEP and low tidal volume (which are part of the whole RM technique) will be continued until the end of the operation.

End of Study

The patients will be monitored throughout the operation and in the postoperative period too (see also the measurements section-primary end point, secondary measurements and follow up). The follow up will last for all the length of hospital stay. The length of hospital stay will be recorded while all the adverse events that will be occurred during this period they will be recorded too. For this kind of population the hospital stay is usually short (<5 days).

Adverse events:

Hemodynamic instability during the RM will be the most important adverse event of the study. During the RM all women should be closely monitored for the occurrence of hypotension or the administration of a fluid bolus or vasopressor medication to support haemodynamic variables. Of course during the whole course of anesthesia the need for vasopressor should be monitored. Possible differences between the two groups should be mentioned for all the above parameters (table 1).

Postoperative lung complications (pneumonia, atelectasis, pulmonary embolism, pneumothorax, acute lung injury (ALI), asthma, non-cardiogenic pulmonary oedema and severe hypercapnia) should also be recorded. As we will mainly include young and healthy population serious lung complications and differences between groups are not anticipated.

Preliminary Data Results

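### The protocol's most important adverse event, haemodynamic instability during the recruitment manoeuvre, has no visible field in its own window: ephedrine and fluids are single undivided totals, and hypotension is not recorded as an event

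*Protocol*

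**What the plan says.** Protocol, Adverse events: "Hemodynamic instability during the RM will be the most important adverse event of the study". Women are to be "monitored for the occurrence of hypotension or the administration of a fluid bolus or vasopressor medication to support haemodynamic variables". Vasopressor need over the whole anaesthetic is added as a further item, and then: "Possible differences between the two groups should be mentioned for all the above parameters (table 1").

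Table 1 lists crystalloids, colloids, blood and "Ephedrine dose (mg") under intraoperative characteristics, with one cell per arm for each. Appendix 3, the data form, has one box per woman for each. Neither is split at delivery or at the RM, and neither has a row for hypotension.

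Anesthetic technique: "The Perioperative use of crystalloids and colloids, blood products and vasopressors will be recorded". Ephedrine is tied there to a mean arterial pressure (MAP) below 60 mmHg, with no restriction to the time after delivery.

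Ventilatory Management: both arms are ventilated identically up to delivery. The RM then lasts about 2 minutes in one arm.

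Secondary measurements and Appendix 5: pressures are taken at baseline (after delivery, before the RM) and at 3, 10 and 20 minutes after the RM. Appendix 5 adds a postoperative column.

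Data Presentation Plan, on these same Table 1 rows: "administration of blood products and intraoperative use of ephedrine should be similar between the two groups (table 1").

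**The concern.** The named event, its recording form and its reporting table do not fit together. The event belongs to a window of about 2 minutes. The table that is meant to show it holds totals that also include whatever was given between induction and delivery, when the RM cannot have caused it. Hypotension itself, the first item to be watched for, has no field. The later scheduled pressures follow any rescue already given, so similar pressures in the two arms would be compatible with a different need for treatment.

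The two sections also set up different readings of the same rows: one expects similarity, the other asks for differences as adverse-event information. At stake is whether the trial can describe the short-term haemodynamic harm of its own intervention. If timing is not on the form, a later analysis plan may be unable to recover it.

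**Working it through.** **1. Does any visible form capture the event in its window?**

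| Item to be watched during the RM | Where it is recorded | Timing available |
|---|---|---|
| Hypotension | No event field; pressures in Appendix 5 | Before the RM; 3, 10, 20 min after; postoperative |
| Fluid bolus | Crystalloid and colloid totals, Appendix 3 and Table 1 | None |
| Vasopressor | Ephedrine total, Appendix 3 and Table 1 | None |

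No row covers the RM itself. The ephedrine row in Table 1 carries a footnote mark whose text is not visible; Appendix 3 still shows a single box.

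**2. What does pre-delivery use do to the mean-dose comparison?**

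The protocol gives no rate, dose distribution or target difference for ephedrine, fluids or hypotension, so there is no plan figure to reproduce. As a check on the power formula used here (two-sample t-test, two-sided 0.05, noncentral t), the protocol's primary-outcome case of d = 0.8 with 34 per group gives power 0.90, as stated.

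Write total dose = pre-delivery + post-delivery. Randomisation and identical management give the pre-delivery part the same expected mean in both arms, so it cancels from the expected difference. If the two parts are independent, the variances add:

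SD(total) = √(SD_post² + SD_pre²), and d = effect / SD(total).

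Assumed, not in the documents: RM effect 4 mg, SD_post 5 mg, independence. From the protocol: 45 per arm, two-sided 0.05.

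| SD_pre (mg) | SD(total) | d | Power |
|---|---|---|---|
| 0 | √25 = 5.00 | 0.80 | 0.96 |
| 3 | √34 = 5.83 | 0.69 | 0.90 |
| 5 | √50 = 7.07 | 0.57 | 0.76 |
| 10 | √125 = 11.18 | 0.36 | 0.39 |

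With an assumed 3 mg effect, power is 0.80, 0.51 and 0.24 at SD_pre of 0, 5 and 10 mg.

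**3. And if women with any use were counted instead?**

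Table 1 does not report this, so it only shows the direction. With a proportion q treated before delivery, independently of later use, the any-use difference is (1 − q) × (p_RM − p_control). Assume 25% vs 5% after delivery, a difference of 20 points. At q = 20, 40 and 60% the difference becomes 0.8 × 20 = 16, 0.6 × 20 = 12 and 0.4 × 20 = 8 points. Here the difference itself shrinks.

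**4. The two readings side by side.**

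The Data Presentation Plan expects similarity in crystalloids, colloids, blood products and ephedrine. Adverse events asks that differences in fluid and vasopressor use be reported, and points to the same table. Pre-delivery amounts fit the first reading and post-delivery amounts the second. A single total cannot serve both.

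**The case against.** The case on the other side has real force on four points.

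- **Bias.** A reader might infer that the totals pull the comparison towards no difference. For the mean dose that Table 1 reports, they do not: randomised pre-delivery use adds variance only. Shrinkage applies to an any-use proportion, which the protocol does not plan to report. This part of the objection stands.
- **Misfiling.** A reader might infer that an excess in the RM arm would be dismissed as a baseline imbalance. The documents do not say so. Adverse events asks for differences to be mentioned, and the Data Presentation Plan refers the reader on to that section. The sentence "If not we will have to mention the differences and this would be a serious limitation of our study" concerns patient characteristics, which have a separate paragraph. Nor is it settled that these rows fall under "Patient and procedural characteristics will be compared between groups using chi-square test for categorical variables and independent-sample t-test for continuous variables", since the same section also names intraoperative variables beside the haemodynamic data. What remains is an unreconciled pair of statements.
- **Size.** With little pre-delivery variation the loss is slight, as the 3 mg row above shows. This stands.
- **Other capture.** Removal for persistent hypotension (MAP below 50 mmHg) would appear among the reasons for not completing, and adverse events are to be recorded throughout the hospital stay. This covers the severe cases. It does not give a count, by arm, of women who became hypotensive or were rescued during the RM and stayed in the study.

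It can also be said that a split at delivery still mixes RM effects with blood loss and other causes. That is true, and it is why a field for the RM window is needed as well as the split.

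**Conclusion.** The concern holds as a recording and reporting gap. On the visible text, the event that the protocol ranks first among its harms has no field in the window where it occurs, and the table named for the comparison holds undivided totals. Only severe cases leading to removal would clearly surface.

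The cost in precision cannot be fixed from the documents. It runs from slight to severe with the amount of pre-delivery use, and the power figures rest on an assumed effect, an assumed SD and independence of pre- and post-delivery doses. Claims of a biased dose comparison, or of a rule that would hide an excess, go beyond the text. The sponsor should make the change because it is cheap and keeps information that the forms as drafted would lose.

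**What to change.** 1. In Appendix 3 and Table 1, split ephedrine, colloid and crystalloid into induction to delivery and delivery to end of surgery.
2. In both arms, add yes/no fields for hypotension, by the protocol's own definition of MAP below 60 mmHg, and for any fluid bolus or vasopressor. Complete each for two periods: the RM or the matching control interval, and delivery to end of surgery.
3. Report the post-delivery items as safety outcomes, with group differences and 95% confidence intervals.
4. In the Data Presentation Plan, limit the expectation of similarity to the pre-delivery amounts, so that it agrees with Adverse events.

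The matching control interval needs one stated clock. The protocol starts the RM one minute after delivery (Abstract), directly after delivery (Ventilatory Management) and 3 minutes after delivery (End of treatment), and these must be reconciled first.

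The cost is a few extra charting fields. Fluids and vasopressors are already to be recorded and arterial pressure is monitored invasively. No dose or rescue rule changes.

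### Within-arm change from baseline in Com_dyn is offered as supporting evidence of efficacy beside the RM-versus-control comparison; it measures change over time and should be descriptive, with efficacy resting on a between-arm contrast that uses baseline.

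*Protocol*

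**What the plan says.** The Efficacy and Safety issues section opens with the between-group aim: Com_dyn "will be statistical significantly improved in the RM group compared to the control group (statistical significant difference between groups", with 20% over control called clinically significant. It continues: "The investigators also believe that there would be statistical significant difference within groups too". For the RM arm it expects this: "In the RM group possibly there would be a difference in lung compliance (increase) between baseline and all the other time points", and it reuses the threshold: "Again a 20% increase in Com_{dyn} would be clinically significant, at least for some patients".

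The abstract (Results and Discussion) makes the same pairing as a forecast. For the RM arm: "In the RM group the investigators estimate that dynamic lung compliance will be significantly higher at all time points (3 minutes, 10 and 20 minutes", measured against baseline. For the other arm: "In the control group there should be no significant difference in dynamic lung compliance at the different time points".

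The Statistical analysis section plans both kinds of test: "Data will be compared between and within groups using Mixed Analysis of Variance (Mixed Anova-General Linear Model". It adds a Bonferroni correction and two-sample t-tests between groups at each time point. The caption of Table 2 says that the reported P-value is the between-subject main effect of the mixed ANOVA. The Measurements section names improvement of Com_dyn as the primary end-point, with readings at baseline (after delivery, before the RM) and at 3, 10 and 20 minutes.

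**The concern.** The null hypothesis of a within-arm test is that compliance does not change between baseline and a later reading. It says nothing about what would have happened without the RM. If compliance moves after delivery for reasons common to both arms, that null is false even when the intervention does nothing. The second 20% benchmark has the same weakness, because it adds shared drift to any treatment effect.

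Nor does a significant change in one arm beside a non-significant change in the other test the difference between the arms. Each arm's result depends on its own noise, and a P-value above 0.05 in controls does not show that they were stable.

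At stake is how the supporting evidence is read. A report could present a rise in the RM arm, a 20% gain and a flat control arm as further confirmation of efficacy, when only the between-arm comparison has the protection of randomisation.

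**Working it through.** **1. The plan's own figure.** Appendix 2 gives n ≥ 2 × (25/20)² × (1.96 + 1.28)² = 2 × 1.5625 × 10.4976 = 32.8, so 33 per group. The exact two-sample t-test with d = 0.8 and two-sided 0.05 has power 0.893 at 33 and 0.902 at 34. The stated minimum of 34 is reproduced. At the 45 randomised per group, power is 0.96. This is a between-group calculation.

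**2. Preliminary data (Table 2, Com_dyn).**
- RM: 33.6 to 51.4, 49.9 and 49.7, so +53.0%, +48.5% and +47.9%.
- Control: 31.1 to 29.6, 30.6 and 30.9, so −4.8%, −1.6% and −0.6%.
- Difference in change at 3 minutes: (51.4 − 33.6) − (29.6 − 31.1) = 17.8 + 1.5 = 19.3 ml/cmH2O. At 10 and 20 minutes it is 16.8 and 16.3.

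These data show no upward drift in controls.

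**3. RM arm alone, 3 minutes, no treatment effect.** From the protocol: 45 per arm and SD 25% of the mean. Assumed: a shared drift of +5% of the mean and within-woman correlation ρ, for which the protocol gives no value. SD of change = 0.25 × √(2(1 − ρ)). Noncentrality = 0.05 × √45 / SD of change. The probability of a significant rise comes from the noncentral t with 44 df. The nominal rate is 2.5%, or 0.83% with Bonferroni over three times.

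| ρ | SD of change | Noncentrality | Unadjusted | Bonferroni |
|---|---|---|---|---|
| 0.5 | 0.250 | 1.34 | 26% | 14% |
| 0.7 | 0.194 | 1.73 | 40% | 24% |
| 0.8 | 0.158 | 2.12 | 55% | 37% |
| 0.9 | 0.112 | 3.00 | 84% | 69% |

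Simulation of the same setting ran up to 85% and 71% at ρ = 0.9, which is simulation error. With +2.5% drift the unadjusted rates are 10% to 31%. With −5% drift, the direction of the preliminary controls, they are 0.05% or less.

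**4. The pattern the abstract describes.** Same setting with +5% drift, 20,000 simulated trials per ρ, compound symmetry:

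| ρ | RM rise at all three times, control change at none: unadjusted | Bonferroni |
|---|---|---|
| 0.5 | 3.9% | 1.7% |
| 0.7 | 5.7% | 3.5% |
| 0.8 | 5.9% | 5.3% |
| 0.9 | 2.3% | 4.6% |

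The looser pattern (RM at one or more times, control at none) occurs in 3% to 25% of trials unadjusted and 9% to 25% with Bonferroni. With +10% drift it falls to 0–6% (0–14% with Bonferroni), and with +20% to about zero, because the controls become significant too. The between-arm t-test of change stays at 4.8% to 5.2%.

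**5. Which between-arm contrast.** Suppose a benefit of d = 0.8 at all three later readings and none at baseline, with 34 per group. If baseline is one of the four readings in the model, as the layout of Table 2 suggests, the main effect averages it in:
- Main effect: d = (0.75 × 0.8) / √((1 + 3ρ)/4).
- Mean of the later readings with baseline as covariate: d = 0.8 / √((1 + 2ρ)/3 − ρ²).
- Mean later reading minus baseline, compared between arms: d = 0.8 / √((1 + 2ρ)/3 + 1 − 2ρ).

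| ρ | Main effect power | Covariate power | Change power |
|---|---|---|---|
| 0.5 | 0.87 | >0.99 | 0.98 |
| 0.7 | 0.79 | >0.99 | >0.99 |
| 0.9 | 0.72 | >0.99 | >0.99 |

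**The case against.** The strongest reply is that no sentence in the protocol lets a within-arm result decide efficacy. RM versus control comes first in the efficacy section, sets the sample size, supplies the supplementary t-tests and underlies every P-value in Table 2. The within-arm lines are forecasts, worded as beliefs and possibilities. This stands, and it limits the point to supporting evidence.

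Two stronger readings are tempting. A reader might infer that the randomised control arm goes unused. The comparisons just listed show that it is used. A reader might also infer that any shared drift would be taken for efficacy. It would not: shared drift cancels in the planned between-arm tests, and a sizeable drift would make controls significant and break the stated pattern.

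The drift itself can fairly be challenged. The only drift in the document is small and downward. Possible causes, such as the single rocuronium dose wearing off or surgery progressing, are conjecture, since the protocol states no effect of either on compliance. The higher rates in step 3 concern one arm at one time point.

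Finally, an analysis plan not shown may name the deciding contrast. That does not remove the point, which rests on what the protocol says: it gives within-arm significance a planned test, a clinical benchmark and a place in the efficacy section.

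**Conclusion.** The point holds in a limited form. The protocol offers within-arm change, with its own 20% threshold and a contrasting non-significant control arm, as supporting evidence of efficacy, and such tests cannot carry that meaning. Bonferroni lowers the rates but does not change the hypothesis being tested.

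The practical risk is modest. It arises mainly for small upward drifts, it does not reach the lead comparison, and the complete pattern appears by this route in only about 2% to 5% of trials with the planned correction. All these rates rest on assumed drift and correlation.

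The choice of between-arm contrast adds a reason to act. Under the plan's own d = 0.8 at 34 per group, a main effect that includes baseline has power of about 0.87 to 0.72 for correlation 0.5 to 0.9, against above 0.99 for the baseline-adjusted comparison. At 45 per group the main effect has 0.95 to 0.83.

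**What to change.** In the abstract, the Statistical analysis section and the Efficacy and Safety issues section, state that improvement in Com_dyn is judged on a between-arm contrast that uses baseline. Either of two forms will do: post-RM values compared between arms with baseline as covariate, or the group-by-time contrast of the planned mixed model (later readings against baseline, RM against control). It should replace the between-subject main effect that averages in the baseline reading. Apply the 20% benchmark to that between-arm difference and report its 95% CI. Report within-arm changes as description without P-values, and stop presenting the expected lack of significant change in controls as supporting evidence.

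The data, alpha and sample size do not change, and the group-by-time contrast comes from the model already planned. The cost is a few sentences and the loss of within-arm P-values as supporting results.
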